The goal of *iCaminemos Juntas!* is to connect Latinas with one another near their neighborhood to encourage increased PA partnerships (e.g., walking). Connections between registered app users will be accomplished through push/pull technology. Push/pull technology describes a style of internet and LBS-based communication where an information transmission request (e.g., "I am interested in going for a walk...is anyone else?") can be initiated by the app user (i.e., "pull") or by the app (i.e., "push"; e.g., a notification sent to an app user indicating that someone would like to walk). Women who are interested in going for a walk can send a request to all other registered app users through the *iCaminemos Juntas!* app. Women who receive a push notification can decline or accept the request. Using LBS, *iCaminemos Juntas!* identifies each assenting user's location and, using LBS algorithms, triangulates each user to one another. Next, using publicly-available geographic information systems (GIS) and LBS data sources,¹⁴²⁻¹⁴⁴ the app determines the location of nearby PA resources (e.g., parks, recreation centers, etc.) that are the best proximal match for the identified users. Users are sent a push notification and map of the PA location. The app requests the user to confirm or decline meeting at this location and sends a meeting location and time confirmation. Using LBS, the app is able to determine whether the user arrived at the designated location. At the user's preferred contact time, the app sends a push notification asking the user to answer four questions: (1) Did you meet a *iCaminemos Juntas!* partner?; (2) Did you walk today?; (3) How long did you walk?; and (4) Did you find the location safe?

The app gathers user profile information, PA preferences, and walking goals. Time- and location-specific notifications are the app's foundation, connecting users and influencing theoretical constructs (e.g., conscious raising, social support) to increase PA. Benefits of using a mobile app include an instantly available source of

social support once a user creates an account, convenience and ease of use, and geographically-relevant information tailored to the user. To ensure users' privacy and safety, the app serves as the "gatekeeper:" Users cannot be located by another user without permission and cannot set up meetings to walk with an unauthorized user. All participants will be fully informed of these privacy policies.

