Usability outcomes: Field usability testing interviews will be recorded, transcribed, and analyzed using Atlas.ti[®] software. Emerging codes will be assigned to phrases and text passages that categorize views, themes, and opinions. The qualitative analysis will rely on constant comparative analysis (based on grounded theory methodology),¹⁵⁵ and a phenomenological approach.^{156,157} To identify problems that impact $\geq 10\%$ of app users^{158,159} with a 95% chance of detection ($\log(1.95)/\log(1.10)$), 28 usability testers are needed. The SUS measure will serve as the primary usability outcome. Additional usability testing outcomes will include app usage data (e.g., log-ins, walks created, etc.). Frequency of responses and proportions and means will be calculated and compared on demographics, using chi-square, t-tests, and correlations, with 2-tailed p=0.05.

3C.4. Experimental Design (Specific Aim 3). The *iCaminemos Juntas!* app will be evaluated in a randomized two-arm, comparative-effectiveness pre-post design. *iCaminemos Juntas!* will be compared to a free and readily available comparison app (*World Walking*, selected because of its primary focus on walking) over 12 weeks. Individuals will be randomized to one of two experimental conditions, using a customized computer program written by KB's biostatistician, [name]. We will recruit a total of 200 community-dwelling Latinas; 100 from the Denver area and 100 from the San Jose area. The primary outcome is change in PA (as measured by the Community Healthy Activities Model Program for Seniors [CHAMPS]¹⁶⁰) relative to baseline. PA was chosen as the primary outcome because Phase I participants strongly expressed that improving their PA level was the main reason why they would use the app.

FIGURE 5: Phase II Study Design

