***iCaminemos Juntas!* only measures:**

Accelerometry and App Usage: Better understanding of the feasibility, accuracy, and added value of accelerometry will inform commercialization efforts. Fitbit® devices will monitor PA for participants who own that device. The Fitbit® will automatically record daily step data in the *iCaminemos Juntas!* app and progress towards the steps/day goal will be graphically presented on the app, using a color-coded graph automatically sent to the participant's phone. For participants who do not own a Fitbit®, the phone's built-in GPS will record the route walked. Data on the time spent during the walk plus the distance derived from the GPS and the walking pace provided by the user in her profile will be combined to estimate steps. *iCaminemos Juntas!* participants will also enter other exercise activities (non-*Caminemos* walks) (minutes/day) using the app. User-entered data will be compared to PA data gathered using the Fitbit® or LBS distance tracking feature.

App usage will be measured by having participants register on the server when downloading the *iCaminemos Juntas!* app. The server will record the number of times (date and time) the app connects to the server and users use various app features (number of uses, initiating walks, accepting walks, app tools used, etc.). Ecological momentary assessment (EMA) will be utilized to evaluate the app's ease of use. EMA's repeated sampling of experiences and behaviors in real time at random intervals should minimize recall bias and increase ecological validity,¹⁸⁸⁻¹⁹⁰ highlight individual differences in behavior and distribution over time, and detect factors affecting behavior.¹⁹¹⁻¹⁹⁵ EMA will be used to assess level of interest and likability of the *iCaminemos Juntas!* app. Participants randomized to that condition will be sent "push notifications" via the app once a week at various times of day that ask them to rate their opinions on the app. Users will also evaluate the app on the System Usability Scale at the 12-week post-test.¹³⁴

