3C.6.3. *iCaminemos Juntas!* Intervention (n=100). A description of the *iCaminemos Juntas!* app was provided in **Section 3C.4.** Participants will download the app following the procedures outlined in **Section 3C.7.1.** Project staff will provide *iCaminemos Juntas!* users a one-one-orientation to the app and how to use its unique features. Daily alerts and notifications will engage users in daily use of the app and provide up-to-date information on users' progress. Participant responses will also be used to evaluate additional or on-going support of users' needs (e.g., increase/ decrease prompts based on user preferences, tailored messages around a set goal, etc.). To protect privacy and to ensure that the participant is the person completing the app activities, KB will uniquely identify the user's smartphone based off the device's "hardware footprint". The app will upload all app activity data to the KB secured web server database.

3C.6.4. World Walking App Comparison Group (n=100). *World Walking* (www.worldwalking.org) is an app available for free on both iOS and Android platforms.¹⁹⁶ It allows users to track walking steps using the phone's LBS features, display walks on a virtual route, create virtual walking groups (you and other users can have shared goals for walking a certain distance such as walking the Great Wall of China), chat with virtual group members, earn badges for meeting goals, connect to Fitbit, and receive push notifications. There are a number of similarities between the two apps; participants will be able to track their walking, have a reward-based system for meeting goals, map their walks, use Fitbit, and have a social network component. The app encourages social interaction by letting walkers form virtual clubs, working together to meet distance targets.

However, while there are similarities between the two apps, *World Walking* will not allow for real-time, in-person social connection (meeting other women in-person and walking locally), or connection to social media.

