Aim 1 will be assessed by examining the number of connections/matches for walking (creating and/or joining a walk). We believe that at least 70% of the *iCaminemos Juntas!* intervention group will establish at least one connection and participate in at least one walk (e.g., 78% of users in Phase I created at least one walk). The distribution of number of connections and walks completed will be examined. We will test whether there is a difference between the groups in connections that occurred using a chi square test and will further test a single proportion that the *iCaminemos Juntas!* group will have significantly more than 70% active participation as evidenced by making at least 1 connection.

Aim 2 will be evaluated descriptively and via feasibility testing showing that location-based services can be replicated regardless of region.

Aim 3 is critical to product development and will evaluate whether *iCaminemos Juntas!* increases physical activity, social support, and quality of life (QOL) in Latinas. Three hypotheses for the comparative-effectiveness trial will be examined:

H₁: Latinas randomized to the *iCaminemos Juntas!* app will report greater improvements in their physical activity compared to Latinas randomized to the comparison app (*World Walking* app) at 12-weeks post-test.

H₂: Latinas randomized to the *iCaminemos Juntas!* app will report greater increases in their social support for exercise compared to Latinas randomized to the comparison app at 12-weeks post-test.

H₃: Latinas randomized to the *iCaminemos Juntas!* app will report greater improvements in their quality of life (QOL) compared to Latinas randomized to the comparison app at 12-weeks post-test.

Additional secondary analyses will (1) evaluate immediate changes in the PA, social and environmental support, and QOL measures at 6 weeks; (2) assess mediators at 6-weeks for a mediational analysis on 12-week outcomes; and (3) evaluate app usage data (e.g., number of log-ins, number of “check-ins”, EMA responses for likability and satisfaction with the app).

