Tests will be performed as per the design using simple t-tests followed by analysis of covariance to assess the outcome results adjusted for baseline (rather than change from baseline). Multivariate analyses will be conducted to assess the simultaneous direction of changes in the components between the treatment arms. We will test the outcomes simultaneously and examine the correlation amongst them within treatment arms. Hotelling’s T² will be used to test the overall mean vector of responses. This analysis will utilize the pre- and post-measures, but additional analyses will be conducted using generalized least squares regression (PROC MIXED in SAS ver 9.3 or higher) to account for missing data (drop outs between 6 weeks and 12 weeks).

Characteristics of dropouts and/or noncompliant individuals (those who do not walk and/or form any connections) will be intensively examined to shed light on potential weaknesses of the app (differential dropout overall or within certain subgroups). The evaluation of the app will include its impact using the pre-post data. As noted, examination of the correlation matrices along with the mean changes will inform whether the variables appear to move similarly in both groups. Thus, one might argue that it is not necessarily the best control choice since we would then be measuring the intensity of intervention. Alternatively, very different correlation structures will inform us about how the interventions are working and may provide information on appropriate controls and or strengths and weaknesses.

Utilization data will be examined to understand the acceptability and intensity of interactions with the apps. The penetration of the apps into this minority at-risk population is very important in potentially understanding, not only market share, but also potential impact. Complier average causal effect models²⁰³ will be used to examine the intensity of the intervention app’s utilization. Mediation models using the latest bootstrapping methods^{204,205} will be examined to enhance evidence that the changes induced by the treatment effects are consistent with the changes being mediated via the app and the intervention.

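### In-person shared walks may correlate outcomes in the app arm only, yet the planned t-test, ANCOVA and 90% power calculation treat all women as independent

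*Combined protocol and SAP*

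**What the plan says.** Section 3C.4 sets the unit of randomisation: "Individuals will be randomized to one of two experimental conditions". The app description just before section 3C.3.1 explains how the test app links those individuals afterwards: "Women who are interested in going for a walk can send a request to all other registered app users". Women who accept are located, matched to a nearby venue and sent there to meet. Section 3C.8 (Aim 1) expects at least 70% of the app arm to use this; its wording is that the "intervention group will establish at least one connection and participate in at least one walk".

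The comparator is different by design. Section 3C.6.4 says that World Walking "will not allow for real-time, in-person social connection (meeting other women in-person and walking locally"), although users can "create virtual walking groups (you and other users can have shared goals for walking a certain distance".

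For the outcomes, section 3C.8 plans "simple t-tests followed by analysis of covariance", the latter adjusting for baseline. PROC MIXED is an additional analysis, and its stated purpose is to deal with dropout. The correlation matrices mentioned there are between outcome measures within an arm, not between women. The sample size rests on a two-sided, unequal-variance t-test. Neither section 3C.8 nor the limitations in section 3C.9 mentions an ICC, a design effect or a cluster-adjusted variance.

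**The concern.** This is individual randomisation with a treatment delivered partly in groups, in one arm only. If social contact raises activity as the plan's theory proposes, a woman's 12-week activity will depend partly on that of the women she walks with. The app-arm mean then varies more than the independence formula allows. Baseline adjustment cannot remove dependence that arises after randomisation. At stake are a primary confidence interval that is too narrow and a power statement that is too favourable. The arm that may cluster also carries the larger planning SD (355.7 against 179.1), so inflation there passes largely into the standard error of the contrast.

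**Working it through.** **Inputs from section 3C.8.** Difference 144.7 min/week; SD 355.7 (test) and 179.1 (comparison); two-sided alpha 0.05; 81 per arm for 90% power; 20% dropout; 100 enrolled per arm, so 100 × 0.80 = 80 evaluable.

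**Assumed, because the documents give no figure.** Walking-group size m of 2 to 5; ICC of 0.01 to 0.10; all app-arm women in groups; no correlation in the comparator arm.

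**Step 1: reproduce the plan.** Under independence, power of the unequal-variance t-test from the noncentral t distribution first reaches 90% at 81 per arm (90.03%). The second scenario (difference 178.0 − 71.5 = 106.5, SDs 234.9 and 179.1) gives 82 (90.04%). Both stated sizes are right if the women are independent. With 80 per arm, power in the first scenario is 89.7%, or 90.1% by the normal approximation used below.

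**Step 2: inflate the app arm only.** The design effect is DE = 1 + (m − 1) × ICC. The true-to-planned standard error ratio is

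R = √[(DE × 355.7² + 179.1²) / (355.7² + 179.1²)].

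With 355.7² = 126,522 and 179.1² = 32,077, the app arm holds 126,522 / 158,599 = 0.798 of the variance, so R = √[1 + 0.798 × (m − 1) × ICC].

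**Step 3: consequences.** If the mean effect is zero, type I error = 2 × [1 − Φ(1.96 / R)]. The independence standard error is √(158,599 / 80) = 44.53. Power with a correct standard error is Φ(144.7 / (44.53 × R) − 1.96).

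| m | ICC | R | Type I error | Power |
|---|---|---|---|---|
| 2 | 0.01 | 1.004 | 5.1% | 90% |
| 2 | 0.05 | 1.020 | 5.5% | 89% |
| 2 | 0.10 | 1.039 | 5.9% | 88% |
| 4 | 0.01 | 1.012 | 5.3% | 89% |
| 4 | 0.05 | 1.058 | 6.4% | 87% |
| 4 | 0.10 | 1.113 | 7.8% | 83% |
| 5 | 0.01 | 1.016 | 5.4% | 89% |
| 5 | 0.05 | 1.077 | 6.9% | 86% |
| 5 | 0.10 | 1.149 | 8.8% | 81% |

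The last row in full: DE = 1 + 4 × 0.10 = 1.40; R = √(1 + 0.798 × 0.40) = 1.149; 1.96 / 1.149 = 1.706, giving 8.8%; 144.7 / 51.14 − 1.96 = 0.87, giving 81%.

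**Step 4: partial grouping and the second scenario.** Simulating 20,000 null trials with 70% of the app arm in groups of 4 gave 5.8% at ICC 0.05 and 7.0% at ICC 0.10, against 6.4% and 7.8% in the table. With the second scenario's SDs, groups of 5 give 6.5% and 8.0% instead of 6.9% and 8.8%.

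These figures are for the t-test on change. ANCOVA would reduce the residual variance but leave the induced correlation. Fixed, non-overlapping groups are an approximation, since partners may change.

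**The case against.** **False positives.** A reader might infer that the primary test's error rate exceeds 5% as a matter of course. The documents do not support that. Groups form after randomisation, by choice and location. Active women pairing with active women produces an observed ICC, but rearranging independent women does not change the variance of the arm mean. If the app alters no one's activity, it induces no correlation and the t-test keeps its level. The inflated rates need partners' activity to move together while the mean effect is exactly zero. This part of the objection stands. The narrow interval and overstated power need only the induced correlation.

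**Size.** One could assume groups of 10 and reach 13.5% at ICC 0.10. Nothing in the text supports groups that large: about 50 app users are expected per city (100 per site, two arms), and Aim 1 asks for only one walk from 70% of them. The outcome also covers all weekly activity, of which app walks are a part. For pairs, or at ICC 0.01, the effect is small.

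**Remedy.** A walking-group random effect in the test arm is the tempting repair, but it gives grouped women less weight than singletons, and the grouping is self-selected. In 3,000 simulated trials with no app effect, no induced correlation and 70% of the arm grouped in fours by a trait correlated 0.5 with activity, that model was biased by about −38 min/week and rejected 9.6% of the time. The t-test was unbiased. The random effect should not be the primary model. Added to PROC MIXED, it would also leave the t-test and ANCOVA as they are.

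**Data.** A reader might assume that the logs show who walked with whom. Section 3C.6.2 lists counts of how "users use various app features (number of uses, initiating walks, accepting walks, app tools used, etc".), and the app detects arrival at the venue. Partner linkage is a reasonable inference, not a stated record.

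**Conclusion.** The point holds as a conditional one. The plan creates a route to correlation in one arm and allows for it nowhere. If shared walking does induce correlation, the planned standard error is too small and the 90% power is overstated. Over groups of 2 to 5 and ICCs of 0.01 to 0.10, with 80 evaluable per arm, the first-scenario SDs and the whole app arm grouped, the standard error is 0.4% to 15% too small relative to the planned value (R of 1.004 to 1.149). Power runs from 90% down to 81%, and type I error, under the narrow null described above, from 5.1% to 8.8%. ICC and group size are assumptions, so the size cannot be settled from the documents; less grouping means less effect. The comparator's virtual groups could add some dependence there too, which these figures ignore. The planned contrast remains a valid estimate. What needs attention is its stated precision, and the change is worth making before analysis.

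**What to change.** In section 3C.8:

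1. Keep the randomised t-test/ANCOVA contrast as the point estimate.
2. Beside it, report a standard error and confidence interval that are cluster-robust in the app arm. Form clusters by a pre-specified rule from logged shared walks, where the logs allow partners to be linked. Treat all other women as singletons.
3. If walks link most women in a city into one network, report instead the contrast with the app-arm variance inflated over ICC 0.01 to 0.10, for a group size stated in advance.
4. Do not make a walking-group random effect the primary model.
5. State that the 90% power assumes no correlation between participants, and give the range above.

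In simulation with 70% of the arm grouped in fours, the robust interval had type I error of 5.5% and 6.0% at induced ICC 0.05 and 0.10, against 5.8% and 7.2% for the planned test. Under pure sorting it had 2% to 4%.

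The cost is a few lines of text, a check that the logs can link partners, and some programming. The interval will be somewhat wider, and conservative if the grouping reflects sorting only. The power statement becomes less favourable. No extra participants, visits or questionnaires are needed.

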Participants will be assisted with downloading the appropriate app, provided instructions on how to use the app (*iCaminemos Juntas!* or *World Walking*), and encouraged to use the app daily.

6-week interim assessment: Participants will complete interim assessments of initial changes. An invitation email and text messages containing a link to the interim surveys along with their unique password (PIN number) will be sent. Participants will complete the web-based surveys using either their computer or smartphone; no in-person meeting will be required. Participants who do not complete the surveys within 3 days will receive an email and text reminder (and 3 more reminders at 3-day intervals if still not completing it).

12-week post-test assessment: Participants will complete an in-person post-test assessment. They will meet individually with a study staff to complete the online surveys on a study tablet and a brief post-test interview.

3C.6.2. Outcomes: Baseline, Interim, and Post-test Measures. The baseline, 6-week interim, and 12-week post-test surveys will use validated scales to measure the primary outcome – physical activity - and secondary outcomes of social and environmental support and quality of life (QOL). Surveys should take 30-45 minutes to complete. See **Table 4** for schedule of measurements.

TABLE 4: Schedule of Measurements

Assessment	Screening	Pre-test/Baseline	Week 6	Week 12/Post-test
Inclusion Screener	X			
Physical Activity		X	X	X
Social & Environmental Support		X	X	X
Quality of Life (QOL)		X	X	X
Usage Data (iCaminemos Juntas! app only)			X	X
System Usability Scale (iCaminemos Juntas! app only)				X

Physical Activity:

The Community Healthy Activities Model Program for Seniors (CHAMPS¹⁶⁰) is a 41-item PA questionnaire that measures self-reported minutes-per-week of PA calculated as total weekly caloric expenditure in all PA. It was developed for underactive populations and validated among older adults.¹⁶⁰ However, CHAMPS has been used with younger and racially/ethnically diverse populations; it is sensitive to change specifically in Latino and other populations including ones younger than senior age.¹⁶⁴⁻¹⁶⁷ The CHAMPS asks about activities undertaken for exercise, daily activities that are physical in nature, and physically active recreational activities during “a typical week in the past 4 weeks.” CHAMPS has strong psychometric properties,^{160,168} including validation in Spanish and sensitivity to change.¹⁶⁹⁻¹⁷¹

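### App use is scheduled for the test app only, so the planned between-group test of connections and the utilisation analysis of both apps have no described comparator-arm data

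*Combined protocol and SAP*

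**What the plan says.** **Measurement.** Table 4 in section 3C.6.2 has the row "Usage Data ( iCaminemos Juntas! app only" at weeks 6 and 12, and the row "System Usability Scale ( iCaminemos Juntas! app only" at week 12. The text on measures specific to the test app agrees with the table:

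- Usage comes from the sponsor's server: "App usage will be measured by having participants register on the server when downloading the *iCaminemos Juntas!* app".
- The weekly in-app ratings have the same scope: "EMA will be used to assess level of interest and likability of the *iCaminemos Juntas!* app".
- On usability: "Users will also evaluate the app on the System Usability Scale at the 12-week post-test".

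The comparator, World Walking (section 3C.6.4), "is an app available for free on both iOS and Android platforms". No data feed from it to the sponsor is described, and no survey item on its use is listed.

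**Analysis.** Under Aim 1, section 3C.8 says "We will test whether there is a difference between the groups in connections that occurred using a chi square test". Later in the same section it says "Utilization data will be examined to understand the acceptability and intensity of interactions with the apps". The sentence after that again speaks of apps in the plural, while the complier average causal effect model in the same paragraph is limited to the intervention app.

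**Adherence.** Section 3C.6.5 takes adherence to be equal in the two arms for want of data suggesting otherwise. It sends weekly text reminders to both arms.

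**The concern.** Two statements in the analysis section call for data on use of the comparator app, and the measurement plan describes no way of obtaining them. One is a named between-group test.

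Interpretation is also at stake. Section 3C.6.4 says the comparator was chosen as a possible market competitor with similar features. If the test arm does better, readers will ask whether the test app is better or whether the competitor was hardly opened. If the arms do not differ, they will ask whether the competitor was used just as heavily. The plan treats fading use as a risk in both arms, since it sends reminders for either app, but a reminder prompts use without recording it.

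**Working it through.** No planning figure in the documents bears on this point. The sample size was checked for completeness. With a difference of 144.7 and standard deviations of 355.7 and 179.1, 81 per arm gives a standardised difference of 144.7 / √((355.7² + 179.1²)/81) = 144.7 / 44.25 = 3.27. The unequal-variance t-test then has 90.03% power, as the plan states. Collecting usage in both arms does not change this.

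**Step 1: possible comparator-arm sources.**

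| Source (section) | Covers the comparator arm? | Records use of the assigned app? |
|---|---|---|
| Server log (3C.6.2) | No | Test app only |
| Weekly in-app ratings (3C.6.2) | No | Opinions of the test app only |
| System Usability Scale (Table 4) | No | Usability, not use |
| CHAMPS (3C.6.2) | Yes | No; total activity, whether or not the app prompted it |
| Social Support for Exercise Survey (3C.6.2) | Yes | No; perceived encouragement |
| Weekly text reminders (3C.6.5) | Yes | No |
| Help with downloading at baseline (3C.6.1) | Yes | Installation only |
| Brief week 12 interview (3C.6.1) | Yes | Content not described |

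Only the interview could supply comparator use, and nothing says that it will.

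**Step 2: the chi-square test of connections.** Its meaning depends on what a connection is.

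- *In-person walks created or joined.* This is how Aim 1 glosses the term. Section 3C.6.4 says that World Walking does not offer in-person connection, so the count made through that app is zero by design, not missing. The test is then uninformative. At the plan's own expectation of 70%, with 100 per arm, the table is 70/30 against 0/100, and χ² = 200 × (70×100 − 30×0)² / (100 × 100 × 70 × 130) = 107.7 on 1 degree of freedom. Rejection is a foregone conclusion and reflects only what the apps permit.
- *Any connection, including virtual groups.* World Walking has such groups, so the count could be above zero. The comparator column then has no described data source.

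Neither reading gives a useful between-group test as planned.

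**Step 3: utilisation of both apps.** Server data exist for up to 100 women in the test arm. Described usage data exist for 0 of the 100 in the comparator arm.

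**Step 4: what the added items would give.** Section 3C.8 plans for 20% dropout, leaving 100 × 0.80 = 80 per arm. The true proportion using the assigned app is unknown, so 0.5 to 0.9 is assumed. The 95% half-widths are 1.96 × √(p(1−p)/80) for one arm and 1.96 × √(2p(1−p)/80) for the difference, with the same p in both arms.

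| Assumed proportion | One arm | Difference between arms |
|---|---|---|
| 0.5 | ±0.110 | ±0.155 |
| 0.7 | ±0.100 | ±0.142 |
| 0.9 | ±0.066 | ±0.093 |

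This is enough to tell a largely unused comparator from a well-used one, but not to show that use was closely similar.

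**The case against.** The strongest reply is that the trial is a randomised comparative-effectiveness comparison. Low uptake of a competitor is then part of that competitor's real-world effect and does not confound the result. This stands. A reader might infer that a difference against World Walking means little unless its use is known, but the documents do not support that. The stated goal concerns effectiveness against a marketed product, and the CHAMPS comparison answers it whatever the uptake.

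Other parts of the reply also stand:

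- The complier average causal effect model is confined to the intervention app and does not need comparator usage.
- The profile of non-compliant women is meant to expose weaknesses of the app, in the singular. It does not clearly promise a comparator-arm profile, and dropout is visible in both arms anyway.
- The System Usability Scale is consistently a test-app measure, and no between-arm analysis of it is planned. Its restriction is not a contradiction.
- Section 3C.8 says utilisation will be examined. It does not say that the apps will be compared on it. The only explicit between-group test here is the chi-square.
- The equal-adherence statement sits in a paragraph on attrition. If it means retention, it can be checked in both arms. Only as a statement about app use can it not.

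It could also be said that the plural in section 3C.8 is loose wording. That is less convincing, because it occurs twice, and the same paragraph names the intervention app alone when only one app is meant.

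**Conclusion.** The point holds as a mismatch between measurement and analysis. The between-group test of connections and the examination of utilisation of both apps have no described data for 100 of the 200 participants. On the narrow reading of a connection, the test has a comparator count fixed at zero by design. Equality of app use between arms cannot be checked, and comparator uptake cannot be used to explain a positive or a null result.

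A reader might go further and conclude that the trial cannot show whether the comparator was used at all. The documents do not support that. Staff help with installation, and the week 12 interview covers both arms and could ask. The accurate statement is that no data source is planned.

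The primary test, its power and the complier analysis are unaffected. The point should be settled before enrolment because it is cheap to fix then and cannot be fully repaired afterwards. It rests on the protocol text available. A description elsewhere of comparator usage data, or of interview questions on app use, would largely close it.

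**What to change.** 1. Add identical self-report items on the assigned app to the week 6 and week 12 surveys in both arms: days per week used, walks logged, any in-person walking partner and, as a separate item, any virtual group joined.
2. Amend the usage row of Table 4 to show these items for both arms. Keep the server logs as a test-arm supplement, where they can also be used to check the self-reports.
3. Define a connection for the Aim 1 chi-square test so that in-person walks and virtual groups are not pooled. Say how the test is to be read, given that the comparator app does not provide in-person matching.
4. If the items are not added, restrict the connection and utilisation analyses in section 3C.8 to the test arm, and state that comparator uptake was not measured.

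Giving the System Usability Scale to both arms is optional.

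The cost is a few minutes of survey time at assessments already scheduled, with no change in sample size. The main drawback is that comparator use would be self-reported. Identical wording in both arms at least allows a like-for-like comparison.
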